Efficacy parameters:	
Tumour response:
 
 
• ORR (primary efficacy endpoint);
 
• DCR; PFS; OS; TTP; TTR; DOR (secondary efficacy endpoints) (only Part 2).
 

Pharmacokinetic parameters:	PK parameters of OMO-103: AUC; C min ; C max ; t max ; t 1/2 .
PD parameters:	Circulating human ADA to OMO-103; Ki67 and CC3 by IHC; Immune infiltration by IHC (CD3, CD4/CD8, PD-1/ PD-L1) and others to be determined; Multiplex assay from biopsies (e.g., MYC-

expression levels); Cytokines and other PD biomarkers for the purpose of an optional genetic analysis and for target validation; PBMC and immune characterisation blood samples only during Part 2 (Dose Expansion).

**Statistical methods:**Sample Size

The sample size is determined based on clinical rather than statistical considerations. For the dose escalation part, up to 24 patients are anticipated to be recruited. The number of patients in this study is consistent with Phase 1 dose finding studies. In Part 2, at least 3 parallel groups of patients with advanced NSCLC, TNBC and CRC will be treated. Approximately 18 patients will be enrolled in each group in Part 2.

General Considerations

In general, all data will be summarised using appropriate descriptive statistics by per dose cohort and for the expansion groups where applicable. Summary tabulations will be presented that display the number of patients (N), number of observations, mean, SD, median, minimum, and maximum for continuous variables, and the number and percent (of non-missing values) per category for categorical data by absolute and relative frequencies.

Unless indicated otherwise, summary statistics will be reported for observed data only. Missing data will not be imputed. If a baseline value is missing, no change from baseline will be calculated.

Baseline is defined as the last assessment before the start of IMP administration.

Safety data will be reviewed continuously and integrated with PK and PD data at the end of dose escalation in order to determine the dose to be administered during the dose expansion part of the study. The same data will be integrated at the conclusion of the study in order to determine the RP2D to be used in future trials of OMO-103.

Interim Analysis

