10 STATISTICAL METHODS

10.1 GENERAL PRINCIPLES

- All statistical methods will be based on the International Conference on Harmonisation (ICH) E9 document “Statistical Principles for Clinical Trials”.
- All data collected will be presented within data listings.
- Generally, data listings will be sorted by subject and by period/regimen where appropriate.
- Generally, data will be summarised by period/cohort. Baseline data will be summarised overall. The format of the summaries is defined in the shells at the end of this document.
- Repeated visits will be denoted with ‘RPT’. Unscheduled visits will be denoted with ‘UNS’.
- In summary and analysis tables of continuous variables, standard descriptive statistics (N [number within analysis set, or group, or subgroup], n [number of observations included in analysis], mean, standard deviation [SD], median, minimum and maximum) will be presented. Least squares means (LSMean) and 95% confidence intervals (CI) will be presented in the

statistical analysis outputs as appropriate. For PK summaries, geometric mean and coefficient of variation (%CV) will also be used to summarise the data.

- Unless otherwise specified, the minimum and maximum statistics will be presented in summary tables to the same number of decimal places as the original data. The mean, median, LSMeans, and CI will be presented to one more decimal place than the original data. SD will be presented to two more decimal places than the original data.
- Derived PK parameters and concentration data listings and summaries will be presented to 3 significant figures (with the exception of CV%, which will be presented to 1 decimal place). The ratio of the geometric LSMeans and its associated confidence interval will be presented to 2 decimal places.
- In summary tables of categorical variables, the number of non-missing observations by category will be presented along with percentages. Unless otherwise specified, the denominator for each percentage will be the number of non-missing observations.
- All percentages will be presented to one decimal place.
- All plots will use a linear time scale for the nominal times of the visits and will be labelled by time point.

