Programming note: A similar table will be presented for Part 2 (Dose expansion)

OMO-103-01
Table 14.1.2.1
Summary of Demographic and Baseline Information - Part 1
Safety Set

Parameter	Statistic	All Subjects (N=x)
Age (yrs)	n	x
	Mean	x.x
	SD	x.xx
	Min	x
	Median	x.x
	Max	x
Height (cm)	n	x
	Mean	x.x
	SD	x.xx
	Min	x
	Median	x.x
	Max	x
Weight (kg)	n	x
	Mean	x.xx
	SD	x.xxx
	Min	x.x
	Median	x.xx
	Max	x.x
Number of pre-treatments per patient	n	x
	Mean	x.xx
	SD	x.xxx
	Min	x.x
	Median	x.xx
	Max	x.x

Source Listing: 16.2.4.1; Produced: yyyy-mm-ddThh:mm - Page x of y

Percentages are based on the total number of subjects within the Safety Set.

Programming note: A similar table will be presented for Part 2.

[Continued overleaf...]

OMO-103-01
Table 14.1.2.1
Summary of Demographic and Baseline Information - Part 1
Safety Set

Parameter		Statistic	All Subjects (N=x)
Race:	BLACK OR AFRICAN AMERICAN	n (%)	x (x.x)
	AMERICAN INDIAN OR ALASKA NATIVE	n (%)	x (x.x)
	ASIAN	n (%)	x (x.x)
	NATIVE HAWAIIAN OR OTHER PACIFIC ISLANDER	n (%)	x (x.x)
	WHITE	n (%)	x (x.x)
	MIXED	n (%)	x (x.x)
	OTHER	n (%)	x (x.x)
Gender:	M	n (%)	x (x.x)
	F	n (%)	x (x.x)

Source Listing: 16.2.4.1; Produced: yyyy-mm-ddThh:mm - Page x of y
Percentages are based on the total number of subjects within the Safety Set.

*Programming note: A similar table will be repeated for 14.1.2.2 (FAS).
A similar table will be presented for Part 2.*

OMO-103-01
Table 14.2.1.1
Summary of Progression Free Survival (PFS) - Part 1
Safety Set

Parameter	Cohort	Statistic	
PFS	Cohort 1 (Dose 0.48 mg/kg) (N=x)	n	x
		Mean	x.x
		SD	x.xx
		Min	x
		Median	x.x
		Max	x
	Cohort 2 (Dose 1.44 mg/kg) (N=x)	n	x
		Mean	x.x
		SD	x.xx
		Min	x
		Median	x.x
		Max	x
	Cohort ...		
	Overall (N=x)	n	x
		Mean	x.x
		SD	x.xx
		Min	x
		Median	x.x
Max		x	

Source Listing: 16.2.7.1; Produced: yyyy-mm-ddThh:mm - Page x of y
Percentages are based on the total number of subjects within the Safety Set.

*Programming note: A similar table will be presented for Table 14.2.1.2 (FAS) and Table 14.2.1.3 (PPS)
All tables will be repeated for Part 2.*

OMO-103-01
Table 14.2.2.1
Summary of Efficacy parameters, DCR, ORR, TTP, TTR and DOR - Part 1
Safety Set

Parameter	Cohort	Component	Statistics	Result
DCR	Cohort 1 (Dose 0.48 mg/kg) (N=x)	DCR	Ratio (%)	x.x %
		Complete Response	N	x
		Partial Response	N	x
	Cohort 2 (Dose 1.44 mg/kg) (N=x)	DCR	Ratio (%)	x.x %
		Complete Response	N	x
		Partial Response	N	x
	Cohort 2 Escalation ...	DCR	Ratio (%)	x.x %

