		Complete Response	N	x
		Partial Response	N	x
	Overall (N=x)	DCR	Ratio (%)	x.x %
		Complete Response	N	x
		Partial Response	N	x
Stable Disease		N	x	
ORR.....				
TTP	Cohort 1 (Dose 0.48 mg/kg) (N=x)		N	X
			Mean	x.x
			SD	x.xxx
			Min	x

Parameter	Cohort	Component	Statistics	Result
			Median	x.x
			Max	X
TTR...	...			
DOR				

Source Listing: 16.2.7.2; Produced: yyyy-mm-ddThh:mm - Page x of y
Percentages are based on the total number of subjects within the Safety Set

*Programming note: A similar table will be presented for Table 14.2.2.2 (FAS) and Table 14.2.2.3 (PPS - Part 2 only)
Recommend one page be given to each of the 6 parameters (then repeated for 3 populations as above)
A similar table will be presented for Part 2 with Overall Survival (OS) included.*

OMO-103-01
Table 14.2.5
Dosing of OMO 103-101 - Part 1
Safety Set

Cohort	Statistic	
Cohort 1	n	x
	Mean	x.x
	SD	x.xx
	Min	x
	Median	x.x
	Max	x
Cohort 2	n	x
	Mean	x.x
	SD	x.xx
	Min	x
	Median	x.x
	Max	x
.....		

Source Listing: 16.2.5.1; Produced: yyyy-mm-ddThh:mm - Page x of y
Percentages are based on the total number of subjects within the Safety Set.

Programming note: A similar table will be presented (within the same table number) for Part 2 Dosing

OMO-103-01
Table 14.2.6
Change from Baseline: Quality of Life Questionnaire - Part 1
Safety Set

<Question's group> (Physical, Emotional, Fatigue, Global)

		COHORT 1 (Dose xx mg/ml) (N=x)	COHORT 2 (Dose xx mg/ml) (N=x)	...	Overall (N=xx)
Baseline	n	xx (xx.x %)	xx (xx.x %)		xx (xx.x %)
	Mean	xx.xx	xx.xx		xx.xx
	SD	xx.xx	xx.xx		xx.xx
	Minimum	xx.x	xx.x		xx.x
	Maximum	xx.x	xx.x		xx.x
	Median	xx.xx	xx.x		xx.xx
Visit	n	xx (xx.x %)	xx (xx.x %)		xx (xx.x %)
	Mean	xx.xx	xx.xx		xx.xx
	Etc				
Change from Baseline to Visit	n	xx (xx.x %)	xx (xx.x %)		xx (xx.x %)
	Mean	xx.xx	xx.xx		xx.xx
	Etc				
Etc					

Source Listing: 16.2.7.5; Produced: yyyy-mm-ddThh:mm - Page x of y
 The denominator for each percentage is the number of patients within the column.
 Physical functioning = sum of Q1, Q2, Q3, Q4 and Q5 scores.
 Emotional functioning = sum of Q21, Q22, Q23, and Q24 scores.
 Fatigue = sum of Q10, Q12 and Q18 scores.
 Global = sum of Q29 and Q30.

Programming note: A similar table will be presented for Part 2.

OMO-103-01
Figure 14.2.6.1
Kaplan-Meier Plot of Time from Start of IMP to TTP
Full Analysis Set

Figure Specifications

Procedure: PROC LIFETEST - survival plot

By: Treatment

x axis: Time

x axis: Label: Time Post-Dose (h)

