x axis: values: As appropriate

Y axis: Survival proportion

Y axis Label: Proportion without TTP

Y axis values: As appropriate

Legend:

(dose) OMO 103-101 (N=X) - linestyle = solid, colour = blue

The number of subjects at risk should be presented (option plots=survival(asterisk)).

Source Listing: 16.2.7.2; Produced: yyyy-mm-ddThh:mm - Page x of y
Censoring occurs where a subject did not record TTP within the study.

This layout also applies to:

Figures 14.2.6.2 (Repeat of above for PPS), 14.2.7.1 (Repeat of above for TTR), 14.2.7.2 (Repeat of 14.2.7.2 for PPS)

OMO-103-01
Table 14.3.1.1
Summary of Treatment Emergent Adverse Events - Part 1
Safety Set

	COHORT 1 (Dose xx mg/ml) (N=x)	COHORT 2 (Dose xx mg/ml) (N=x)	Overall (N=x)
Number (%) of subjects with TEAE by grade and relationship to study drug:				
GRADE 1	x (x.x)	x (x.x)	x (x.x)	x (x.x)
NOT RELATED	x (x.x)	x (x.x)	x (x.x)	x (x.x)
POSSIBLY RELATED	x (x.x)	x (x.x)	x (x.x)	x (x.x)
RELATED	x (x.x)	x (x.x)	x (x.x)	x (x.x)
GRADE 2	x (x.x)	x (x.x)	x (x.x)	x (x.x)
NOT RELATED	x (x.x)	x (x.x)	x (x.x)	x (x.x)
POSSIBLY RELATED	x (x.x)	x (x.x)	x (x.x)	x (x.x)
RELATED	x (x.x)	x (x.x)	x (x.x)	x (x.x)
GRADE ...	x (x.x)	x (x.x)	x (x.x)	x (x.x)

Source Listing: 16.2.8.1; Produced: yyyy-mm-ddThh:mm - Page x of y

A subject with multiple adverse events is counted only once at the maximum level of severity or the strongest relationship to study drug.

Percentages will be calculated from the number of subjects in the Safety Set within a cohort.

Programming note: A similar table will be presented for Part 2, with the column headers for each of the 3 groups. A similar table will be presented for Table 14.3.1.1a replacing patient counts by AE event counts.

OMO-103-01
Table 14.3.1.2
Summary of Treatment Emergent Adverse Events by System Organ Class and Preferred Term - Part 1
Safety Set

System Organ Class Preferred Term	Number of Events / Subjects (%)			
	COHORT 1 (Dose xx mg/ml) (N=x)	COHORT 2 (Dose xx mg/ml) (N=x)	Overall (N=x)
Any TEAEs	x / x (x.x)	x / x (x.x)	x / x (x.x)	x / x (x.x)
<SYSTEM ORGAN CLASS TERM> <PREFERRED TERM> <PREFERRED TERM>	x / x (x.x) x / x (x.x)	x / x (x.x) x / x (x.x)	x / x (x.x) x / x (x.x)	x / x (x.x) x / x (x.x)

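### The footnote to the response-rate shell (SAP Table 14.2.2.1) bases cohort and tumour-group percentages on the whole Safety Set, and the cohort DCR blocks show no stable-disease row

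*SAP*

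**What the plan says.** **The response-rate shell.** SAP section 15, Table 14.2.2.1 (Part 1, Safety Set) gives DCR as a percentage ratio for each cohort and for Overall. ORR follows in abbreviated form. Each block carries its own N. The footnote is "Percentages are based on the total number of subjects within the Safety Set". Programming notes reuse the layout for the FAS (14.2.2.2), the PPS (14.2.2.3, Part 2 only) and Part 2, and do not say that the footnote changes.

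**Other denominators in the SAP and protocol.**
- Adverse-event shells, section 15: "Percentages will be calculated from the number of subjects in the Safety Set within a cohort".
- Quality-of-life shell, Table 14.2.6: "The denominator for each percentage is the number of patients within the column".
- General rule, SAP 10.1: "Unless otherwise specified, the denominator for each percentage will be the number of non-missing observations".
- Protocol synopsis, General Considerations: "the number and percent (of non-missing values) per category for categorical data".

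**Component rows.** Under DCR, the Cohort 1, Cohort 2 and following cohort blocks list complete response and partial response. "Stable Disease" appears once, in the Overall block.

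**Status of the endpoints.** The protocol synopsis makes ORR the Part 2 primary endpoint. SAP 1.2 replaces it with progression-free survival (PFS). SAP 11.3 lists ORR and DCR as secondary and says efficacy is summarised descriptively. It gives no numerator, denominator or rule for non-evaluable patients.

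**The concern.** A response rate for a cohort or tumour group should be divided by the patients in that cohort or group. The footnote gives the size of the whole analysis set instead. Elsewhere in section 15 the SAP states a cohort or column base explicitly, so a programmer comparing footnotes could fairly conclude that the response tables are meant to differ.

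Two further problems follow from the same shell. Carried unchanged into the FAS and PPS tables, the footnote names a population other than the one in the table title. And if the cohort DCR line is built from the rows displayed beneath it, cohort DCR omits stable disease while Overall DCR includes it.

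What is at stake is the accuracy of the group-level ORR and DCR in the study report. Double programming (SAP section 12) is weak protection against an error in the specification, because both programmers work from the same shell.

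**Working it through.** **Inputs.** SAP 3.4: about 18 patients in each of 3 Part 2 groups, up to 54 in Part 2, 11 to 24 in Part 1, up to 78 in total. SAP 3.1: one evaluable patient at each of the first two dose levels, then 3+3. The response counts, and the PPS and non-evaluable counts below, are assumptions for illustration; the documents give none.

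**1. The plan's own totals.** 3 × 18 = 54 and 54 + 24 = 78, as stated. Five dose levels at minimum size give 1 + 1 + 3 + 3 + 3 = 11, also as stated.

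**2. Part 2 denominator.** Group rate = x / n_group. Literal footnote = x / N_total. The understatement factor is N_total / n_group.

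| Assumed responders in one group of 18 | Group base (18) | Part 2 total (54) | Whole study (78) |
|---|---|---|---|
| 3 | 16.7% | 5.6% | 3.8% |
| 6 | 33.3% | 11.1% | 7.7% |
| 18 | 100.0% | 33.3% | 23.1% |

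The factor is 54/18 = 3.0, or 78/18 = 4.3 on the whole-study base. The 78 base is included because SAP 6.2 defines the Safety Set without splitting it by Part. The Overall row is unaffected if the base is that Part's Safety Set.

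**3. Part 1 denominator.** One responder in a cohort of 3 is 1/3 = 33.3%. On the Part 1 total it is 1/11 = 9.1% to 1/24 = 4.2%. One responder in a one-patient cohort is 100% against the same 9.1% to 4.2%.

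**4. Reuse for FAS and PPS.** Assume 14 of a group's 18 treated patients are in the PPS, with 3 responders among them. On the PPS base the rate is 3/14 = 21.4%. On that group's Safety Set it is 3/18 = 16.7%.

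**5. If the footnote is set aside.** The default in SAP 10.1 then applies and drops missing observations. With 2 of 18 assumed to have no response assessment, 3 responders give 3/16 = 18.8% instead of 3/18 = 16.7%.

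**6. Stable-disease row.** Assume 0 CR, 2 PR and 6 SD in 18 patients.
- DCR with stable disease: (0 + 2 + 6)/18 = 44.4%.
- Sum of the displayed cohort rows: (0 + 2)/18 = 11.1%, which is also the ORR.
- Displayed rows on the literal Part 2 base: 2/54 = 3.7%.

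**7. Where the footnote has effect.** The same sentence stands under the demographics shell, which has a single all-subjects column, so it is correct there. It also stands under the PFS and dosing shells, which show no percentages. It can therefore produce a wrong number only in the response-rate shell and its repeats.

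**The case against.** The strongest reply is that the footnote is template text. It recurs under shells with no percentages, and it can be read as merely naming the analysis set. Each cohort block has its own N, and SAP 10.1 lets N stand for a group or subgroup. Section 12 requires visual review as well as double programming, and a row showing 3 responders, N = 18 and 5.6% would look wrong. Section 15 also allows layouts to be revised and footnotes to be added. All of this stands as a reason to expect that the cohort base was meant. It does not make the footnote right, and a denominator should be fixed before the data are seen.

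A reader might infer more than the documents support:

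- **That group rates will be understated.** The blocks' own N permits the cohort reading, so this happens only if the footnote is programmed literally.
- **That cohort DCR will collapse to ORR.** DCR has its own ratio line, and an absent display row does not change how a ratio is calculated. The Overall block points to CR + PR + SD. The table was also read from PDF and its stable-disease line is displaced, so loss in reading cannot be excluded. Against that, three cohort blocks consistently lack the row, while the PFS shell, displaced in the same way, keeps all its cohort rows.
- **That the primary analysis is at risk.** ORR is primary only in the protocol synopsis; the SAP makes PFS primary.
- **That SAP 10.1 is a directly conflicting rule.** It yields to any other specification, and a table footnote is one. The protocol's rule is likewise stated as a general one.

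Only the protocol synopsis was available, and SAP 4.2 refers to the protocol body for response criteria. A written DCR definition may exist there, so its absence is not claimed as a defect of the whole plan.

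**Conclusion.** The concern holds in conditional form. The footnote in Table 14.2.2.1 states a base that does not fit a per-cohort rate and differs from the base used in the adverse-event and quality-of-life shells. It also names the wrong population if carried into the FAS and PPS tables. Programmed literally, it understates each Part 2 group's ORR and DCR threefold, assuming 3 groups of 18 and a base of 54; the factor is larger if the whole study is the base.

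The stable-disease point is narrower. As the shell reads in the available text, its components are inconsistent between the cohort and Overall blocks, and cohort DCR could be programmed as CR + PR.

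The consequence is limited to secondary, descriptive results. The Part 2 interim rule in SAP section 8 asks whether any response has been seen and does not use these percentages. The shells should still be corrected before programming, because this is a stated rule that gives a wrong figure when followed.

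**What to change.** In Tables 14.2.2.1 to 14.2.2.3 and their Part 2 versions:

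1. Replace the footnote with: *Percentages are based on the number of subjects in the stated analysis set within that cohort or tumour group (Overall: within that Part).* A base of all treated patients would suit only the Safety Set version.
2. State ORR = (CR + PR)/n and DCR = (CR + PR + SD)/n, with n as in item 1. Keep non-evaluable patients in n, and say that this overrides the non-missing default in SAP 10.1.
3. Show the stable-disease row in every cohort and group block, as in Overall.

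In Tables 14.2.1.1 to 14.2.1.3 (PFS), delete the percentage footnote, since there is nothing for it to act on.

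The cost is shell wording and one added row per block where it is missing. No new data are needed, and neither the analysis sets nor the sample size changes.

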3 STUDY DESIGN

3.1 OVERVIEW

This study is an open label, two-part, FIH Phase 1/2a dose-finding study designed to determine the safety, tolerability, PK, PD and proof-of-concept of OMO-103 in patients with advanced solid tumours.

The study consists of two parts:

Part 1 - General

- Dose escalation in patients with solid tumours, including 5 or more OMO-103 dose levels. Approximately 11 to 24 patients in total will be enrolled in Part 1, covering 5 or more dose levels with the primary objective of determining the safety and tolerability of OMO-103 and defining an appropriate dose for further evaluation in Part 2.

The study will start with an accelerated-titration dose-escalation scheme enrolling one evaluable patient per cohort for the first 2 dose levels followed by a classic 3+3 design.

Part 1 - Timings and assessments

- Screening period: 28 days to 1 day prior 1st dose
- Treatment period:
 - Cycle 1 (Dose-limiting toxicity [DLT] period): CID1, CID2, CID3, CID4, CID5, (Days 3 to 5 only from dose level 3 onwards for PK evaluation), CID8, CID15, CID16/CID17 (Biopsy)
 - Cycle 2: C2D1, C2D8, C2D15
 - Cycle 3*: C3D1, C3D2, C3D3, C3D4, C3D5, (Days 3 to 5 only from dose level 3 onwards for PK evaluation), C3D8, C3D15
- *NOTE: Assumed 3 cycles but these are unlimited
- End-of-treatment (EOT) visit
- Follow-up period: 1-Month Follow-up visit

[figure not shown]
Part 2 - General

- Dose expansion where at least 3 parallel groups of patients with advanced Non-Small Cell Lung Cancer (NSCLC), Triple-Negative Breast Cancer (TNBC) and Colorectal Cancer (CRC) will be treated at the RP2D of OMO-103 to further characterise the safety, tolerability, PK, PD and anti-tumour activity of OMO-103.
Approximately 18 patients will be enrolled in each of the 3 parallel groups of patients (NSCLC, TNBC, CRC) in Part 2.

Part 2 - Timings and assessments

- Screening period: 28 days to 1 day prior 1st dose
- Treatment period:
 - Cycle 1: CID1, CID2, CID3, CID4, CID5, CID8, CID15
 - Cycle 2: C2D1, C2D8, C2D15, C2D16/C2D17 (Biopsy)
 - Cycle 3: C3D1, C3D2, C3D3, C3D4, C3D5, C3D8, C3D15,
 - Cycle 4: C4D1, C4D8, C4D15,
 - Cycle 5: C5D1, C5D8, C5D15,
 - Cycle 6*: C6D1, C6D2, C6D3, C6D4, C6D5, C6D8, C6D15,
- *NOTE: Assumed 6 cycles but these are unlimited
- EOT visit
- Follow-up period: 6-Month Follow-up period, including monthly visits if feasible. Telephone visits may be allowed if considered appropriate, e.g. hospice patients

Parts I/2 – Study Flowchart

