4 STUDY VARIABLES AND COVARIATES

4.1 PRIMARY VARIABLES

The primary endpoints are as follows:

Part 1: Dose Escalation:

- Number of patients with a DLT;
- Number of patients with ≥ 1 related AE;
- Number of patients discontinuing study treatment due to related AEs.

The RP2D will be determined at the conclusion of Part 1.

Part 2: Dose Expansion

- Progression free survival (PFS) based on RECIST v1.1 as assessed by the Investigator.

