8 INTERIM ANALYSES

There will be an interim analysis performed at the end of Part 1.

In the dose expansion part, after half of the patients in all groups (i.e. 9 patients per group) have been included and treated for 3 cycles, efficacy and safety will be analysed. If no response (as per RECIST v1.1) is seen during the interim analysis for at least one patient regardless of group, or for safety reasons, recruitment could be stopped (or the dose reduced) following discussion between the Investigator, the SMC and the Sponsor.

If there are no safety concerns and a response is seen, the study will continue until 18 patients have been recruited in each group.

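### Part 1 related-AE counts and subject-level TEAE tables by dose cohort have no common observation window, so an early end-of-Part-1 cut can understate AEs in the cohort enrolled last

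*SAP*

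**What the plan says.** SAP 4.1 lists three primary counts for Part 1: "Number of patients with a DLT", "Number of patients with ≥ 1 related AE" and "Number of patients discontinuing study treatment due to related AEs". The first is tied to Cycle 1, which SAP 3.1 labels as the DLT period. The other two carry no time limit.

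SAP 11.5.1 counts a TEAE from first use of the drug and gives no end date. On treatment length, SAP 3.1 says of Part 1: "Assumed 3 cycles but these are unlimited". Dose levels open one after another, with one evaluable patient at each of the first two and a 3+3 scheme from the third.

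The shells in SAP 15 give each dose cohort its own column. For the subject-level tables (14.3.1.1 to 14.3.1.5, leaving aside the event-count versions 14.3.1.1a and 14.3.1.2a) the footnote reads "Percentages will be calculated from the number of subjects in the Safety Set within a cohort".

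On timing, SAP 8 says "There will be an interim analysis performed at the end of Part 1", and SAP 4.1 says "The RP2D will be determined at the conclusion of Part 1". Neither the SAP nor the protocol synopsis gives a data cut-off or minimum follow-up for that analysis. The synopsis adds that this interim has no bearing on the escalation rules or on whether Part 2 opens.

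**The concern.** A cumulative percentage can be compared between cohorts only if the cohorts were observed for similar times. Here they open in sequence and patients may stay on drug indefinitely, so an early cut gives the first cohorts more potential observation than the last. The cohort enrolled last is often the highest dose. A flat toxicity profile could then look as if it falls with dose, and a rising one could look flat.

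Nothing in the SAP's list of outputs corrects for this. No TEAE table is restricted to a period common to all cohorts or uses exposure time. The DLT count does have a common window, but the list in SAP 14 contains no DLT table or listing. The open-ended tables are therefore the only AE summaries by dose that the SAP specifies.

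Safety and tolerability is the primary objective of Part 1, so this affects how its main result will be described.

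**Working it through.** **Cohort sizes.** The planned scheme reproduces the lower bound of Part 1: 2×1 + 3×3 = 11. The upper bound of 24 follows if the first two levels grow to three patients each and the other three to six: 2×3 + 3×6 = 24. With single patients at the first two levels the maximum would be 2×1 + 3×6 = 20. The total is 24 + 3×18 = 78, as stated. Cohorts from level 3 upward therefore hold about 3 to 6 patients.

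**Inputs for the bias check.** The documents give no AE rate, retention or cut-off, so these are assumptions:
- q: probability of a first related AE per 3-week cycle, the same at every dose.
- s: probability of staying on treatment from one cycle to the next.
- K: number of cycles observable at the cut. With one 3-week DLT window per level and a cut when level 5 completes Cycle 1, K = 1 at level 5, 3 at level 3 and 5 at level 1.

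**Formula.** Expected proportion with a related AE = sum over k = 1 to K of q × [(1 − q) × s]^(k−1). With s = 1 this is 1 − (1 − q)^K.

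Examples at q = 0.20, K = 5:
- s = 1: 1 − 0.8^5 = 0.672.
- s = 0.6: 0.20 × (1 − 0.48^5)/(1 − 0.48) = 0.375.
- Front-loaded risk, with later cycles at one fifth of Cycle 1 (0.04) and s = 0.8: 0.20 + 0.64 × 0.04 × (1 + 0.768 + 0.768² + 0.768³) = 0.272. Here 0.64 = 0.8 × 0.8 and 0.768 = 0.96 × 0.8.

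| Same true risk at every dose | K = 1 | K = 3 | K = 5 |
|---|---|---|---|
| 20% per cycle, no dropout | 20% | 48.8% | 67.2% |
| 20% per cycle, s = 0.8 | 20% | 41.0% | 49.6% |
| 20% per cycle, s = 0.6 | 20% | 34.2% | 37.5% |
| 20% in Cycle 1, then 4%, s = 0.8 | 20% | 24.5% | 27.2% |
| Risk in Cycle 1 only | 20% | 20% | 20% |

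At q = 0.10, one cycle shows 10%; five cycles show 41.0%, 28.8% and 20.7% for s = 1, 0.8 and 0.6. At q = 0.30, one cycle shows 30%; five cycles show 83.2%, 64.4% and 51.0%.

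**Masking.** With no dropout, 20% per cycle over three cycles gives 1 − 0.8³ = 48.8%. A dose with about 49% risk per cycle, seen for one cycle, would show the same figure.

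**In a cohort of three.** With q = 0.20, s = 0.8 and independent patients, the chance of seeing no related AE is 0.8³ = 0.512 after one cycle and (1 − 0.410)³ = 0.205 after up to three.

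**With a Cycle 1 window.** Equal true risk in Cycle 1 gives equal expected percentages in every cohort (20% and 20% at q = 0.20), whenever the data are cut, provided each patient's Cycle 1 is complete.

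**The case against.** A reader might infer that the highest dose must look safer by construction. The documents do not support that:
- The shortfall is in potential time and depends on when the data are cut. The end of Part 1 is not defined, and the protocol body, which was not available for this check, may define it. SAP 9.4 runs the final outputs after database lock. If all Part 1 patients are then off treatment and followed up, the imbalance in potential time disappears.
- In a 3+3 scheme a lower level may be expanded after DLTs, so the last patients enrolled need not be at the top dose.
- Actual time on drug depends on progression and withdrawal, and these patients have advanced disease.
- A true dose effect, or AEs that begin early, can outweigh the bias.

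A reader might also infer that the recommended dose will be chosen on biased percentages. The synopsis bases the Part 2 dose on continuous safety review together with PK and PD data. Nothing says the dose is picked by comparing cumulative TEAE percentages.

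Nor does the point reach every AE output. Table 14.3.1.2a divides by events, and AEs leading to withdrawal are listed patient by patient.

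Part of the case concerns materiality. Levels 1 and 2 plan one evaluable patient each, so their percentages would be 0 or 100. In cohorts of 3 to 6, one patient moves the figure by 33 to 17 points. Dosing is summarised by cohort (Table 14.2.5), and cycles and onset dates are listed per patient, so a careful reader could piece the exposure together.

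All of this limits the claim. It does not remove it. The dosing shell names no measure or unit, cycle counts appear only in a listing, and neither is linked to the AE tables. An event denominator does not adjust for exposure. No stated cut-off rules out the early-cut case.

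**Conclusion.** The concern holds in a conditional form. The related-AE and discontinuation counts and the subject-level TEAE tables are open-ended. If the end-of-Part-1 cut comes while later cohorts are early in treatment, the cumulative percentages of the cohort enrolled last can be understated relative to earlier ones.

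The size rests on assumed values. At equal 20% risk per cycle, the gap between one and up to five cycles runs from 7.2 points (front-loaded risk, 80% retention) to 47.2 points (constant risk, no dropout). Between one and three cycles, the relevant contrast for levels 3 and 5, it runs from 4.5 to 28.8 points. It is zero if risk is confined to Cycle 1 or all patients have completed treatment and follow-up.

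The DLT count, the escalation rules and the decision to open Part 2 are not touched. What is affected is the description of tolerability by dose at that analysis and, unless follow-up is complete by then, in the study report, mainly from dose level 3 upward. This calls for a worthwhile, inexpensive improvement. It is not a defect that invalidates Part 1.

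**What to change.** In SAP 11.5.1:
1. Add a table by dose cohort of TEAEs and related TEAEs with onset in Cycle 1 (Days 1 to 21). Use the Safety Set and show the number completing Cycle 1 in each column, since the SAP defines no DLT-evaluable set. Base between-dose statements on this table.
2. State the data cut-off for the end-of-Part-1 analysis, in SAP 8 as well.
3. Keep the cumulative tables, with median (range) cycles or time on treatment in each column header.

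An exposure-adjusted rate of first related TEAE, with time to first event or censoring as the denominator, is optional. It adds little in cohorts of 1 to 6 and presumes roughly constant risk.

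The cost is some SAP wording, one extra table and fuller column headers, all from onset dates, visit dates and cycle counts already planned for listing. Cycle 1 counts omit late events, which the cumulative tables still show.
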